MDAnderson Cancer Center

Protocol Abstract Page

A Phase II Study of Carfilzomib in the Treatment of Relapsed/Refractory Mantle Cell Lymphoma 2013-0259

Study Chairman:	[name]
Department:	Lymphoma/Myeloma
[contact]
Unit:	429
Full Title:	A Phase II Study of Carfilzomib in the Treatment of Relapsed/Refractory Mantle Cell Lymphoma
Protocol Phase:	Phase II
Version Status:	Terminated 12/21/2017
Version:	09
Document Status:	Final

Core Protocol Information

Abstract

Objectives:

PRIMARY OBJECTIVE:

- To evaluate the efficacy of single agent carfilzomib in patients with relapsed/refractory MCL as measured by response rate.
- To further evaluate the toxicity of Carfilzomib in patients with MCL.

SECONDARY OBJECTIVES:

• To estimate the response duration, progression free survival, time to failure and overall survival.

Rationale: (Be as concise as possible)

Study Rationale

MCL is a distinct subset of B-cell non-Hodgkin's lymphoma (NHL) characterized by the t (11, 14) chromosomal translocation, which results in over-expression of cyclin D1 and deregulation of the cell cycle. MCL is not yet curable because most patients eventually relapse and succumb to progressive MCL. Therefore, novel therapeutic strategies are needed for the treatment of patients with MCL.

Carfilzomib, an irreversible proteasome inhibitor with selectivity for the chymotrypsin-like

active site, inhibits the proliferation of human tumor cells. In our laboratories, carfilzomib induced apoptosis of both established MCL cells and fresh primary MCL cells from patients in a dose-dependent manner. Carfilzomib significantly inhibited the growth of subcutaneous tumors and prolonged the long-term survival of the MCL-bearing SCID mice. Therefore, Carfilzomib is effective in vitro and in vivo in preclinical studies.35,36

Based on the above data and observations, we propose the current LOI for a phase II clinical trial using carfilzomib in relapsed refractory MCL. We hypothesize that this agent may result in a high CR and PR response rates and have significantly reduced side effects. This protocol aims to evaluate the safety of carfilzomib as single agent in patients MCL and to observe the response rate to this regimen.

Eligibility: (List All Criteria)

Inclusion:

- 1) Confirmed diagnosis of mantle cell lymphoma.
- 2) Patients must have relapsed or refractory MCL.
- 3) Understand and voluntarily sign an IRB-approved informed consent form.

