http://www.fda.gov/ohrms/dockets/AC/04/briefing/4028B1_05_NIH-Inclusion%20of%20Children.doc http://www.hhs.gov/ohrp/policy/populations/children.html

Studies that exclude children must have appropriate justification. Please select all that apply:

Phase I or Phase II study targeting cancer that is very unusual in pediatrics (e.g., prostate, lung, breast, chronic lymphocytic leukemia, etc.)

Are	participan	ts >65 years	s of age eligible t	o participate in th	nis study?		Yes	\bigcirc	No
	pa:	to ve your	, e. age engiale i			-		\sim	

Are pregnant women eligible to participate in this study? O Yes • No

Will the recruitment population at M. D. Anderson include persons who are incarcerated at time of enrollment (e.g., prisoners) or likely to become incarcerated during the study? ○ Yes ● No

Disease Group:

Lymphoma

Treatment Agents/Devices/Interventions:

Carfilzomib

Proposed Treatment/Study Plan:

Is treatment assignment randomized?	Yes	lacksquare	No
-------------------------------------	-----	------------	----

Is this a blinded or double-blinded study? \bigcirc Y	es		No
---	----	--	----

This will be a single-center, phase II clinical trial in patients with relapsed refractory mantle cell lymphoma.

Carfilzomib will be given at a dose of 20*/56 mg/m² (* CFZ 20 mg/m² IV on Days 1 and 2 in Cycle 1 followed by 56 mg/m² for each subsequent dose thereafter) on days 1 and 2, 8 and 9, 15 and 16 of a 28-day cycle (following cycle 12 carfilzomib will be given on days 1 and 2 and 15 and 16 only). The targeted enrollment according to our statistical design is 60 patients.

All patients shall be registered with CORe (Clinical Oncology Research System) at [contact] prior to receiving therapy.

Carfilzomib will be administered intravenously (IV) at $20/56 \text{ mg/m}^2$.

Overall response rate (ORR) (\geq partial response [PR]) will be assessed by the Revised Response Criteria for Malignant Lymphoma, with secondary assessment of clinical benefit response (CBR = minimal response [MR] + ORR), time to progression (TTP), and duration of response (DOR).

Therapy will continue in 28-day cycles for a maximum of 36 cycles (3 years), until there is disease progression, unacceptable toxicity or the patient chooses to withdraw from therapy.

All patients will be asked to record the medications they take at home and to bring the medication record they use to the clinic with them when they return to see their physician or

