15 TABLE OF ASSESSMENTS

Assessment	Screening		Cycles 1 - 12 (cycle = 28 days)		Cycle 13					
	-30 days	Day 1* (+/- 3 days)	Day 2 (+/- 3 days)	Day 8 (+/- 3 days)	Day 9 (+/- 3 days)	Day 15 (+/- 3 days)	Day 16 (+/- 3 days)	and higher	End of Treatment ¹⁶	LTFU
Medical/RX history ¹	х							y.		
Physical exam, ECOG, BSA ²	х	Х		(X) ²		(X) ²		only.	X	
Vital signs ³	х	х	х	х	х	Х	х	16	X	
Neurologic assessment ⁴	х	Х						The second	X	
12-lead ECG	х							15 a	X	
Hematology ⁵	х	х		(X) ⁵		(X) ⁵		2and	X	
Full serum chemistries ⁶	х	Х		(X) ⁶		(X) ⁶		5	X	
Serum β2 microglobulin ⁶	х							1.1		
Hepatitis B and C ⁶	х							day 12		
Coagulation tests ⁷	х							- 1 o	Х	
Pregnancy test ^{8,9}	х	X ⁸		(X) ⁸		(X) ⁸		es [X ⁸	
Tissue and cytology Dx of MCL ¹¹	х							s given lations cycles i		
CT chest/abd/pelvis/neck ¹⁰	х	(X) ¹²						a di se	X	
CXR ¹⁰	х							higher, carfilzonib is given on days 1, All other evaluations remain the same as cycles 1 - 12	X	
Echo/MUGA	х	(X) ¹⁸						a de la		
Unilateral BMB and aspirate	X ¹³	(X) ¹³							X	
Colonoscopy/GI endoscopy	X ¹⁴	(X) ¹⁴						15 ×	X	
Other imaging/PET ¹⁴	х	(X) ¹⁴						12	X	
Carfilzomib administration ^{10,15}		Х	х	х	х	Х	х	hand		
Adverse events								13ar		
Concomitant medications								-		+
Disease status and survival								Cycles		X ¹⁷

(X) Parentheses indicate that the particular test is situational at that time point, as specified in the respective footnote.

- + 3 day window does not apply to Day 1 of Cycle 1
- 1. Medical history: prior treatments for mantle cell lymphoma, significant medical conditions, neuropathy history
- Physical examination: review of systems, height at baseline, weight, calculation of BSA at baseline and if significant weight loss or gain. Abbreviated PE on day 8 and 15 of cycle 1 and days 1 and 15 of cycles 2 and 3 followed by day one of each cycle or as clinically indicated.
- 3. Vital signs: systolic and diastolic blood pressure, respiration, pulse, oral temperature prior to and one hour following carfilzomib infusion during Cycle 1 days 1 and 2 and as clinically indicated. Monitor according to institutional guidelines with each dose of carfilzomib.
- 4. Neurologic exam: evaluate peripheral neuropathy and/or changes in preexisting neuropathy

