- 13. Send baseline bone marrow aspirate for cytogenetics and lymphoma markers. FISH for IgH/cyclin D1 may be required to make a definitive diagnosis if bone marrow is inconclusive. Repeat only if initially positive and send bone marrow aspirate for lymphoma markers. Repeat bone marrow biopsy to confirm CR.
- 14. Baseline colonoscopy and other GI endoscopies are required only if this is the main area of disease response assessment. They do not need to be repeated on C1D1. If in CR by radiologic evaluation, bone marrow or blood test at any time, do colonoscopy with random biopsy and bone marrow biopsy and PET scan if necessary and possible to confirm CR.
- 15. Carfilzomib administration: See section 6 for pre-treatment therapy and study drug administration and section 7 for dose modification guidelines.
- 16. Approximately 30 days after discontinuation of all study drugs or before start of subsequent treatment (whichever occurs first)
- 17. Every 6 months for 1 year via telephone. For subjects who did not progress during treatment.
- 18. ECHO/MUGA can be done as needed at any other time with cardiac consultation. They do not need to be repeated on C1D1.

Study Enrollment:

The study population for this research will consist of participants from:

Only at MDACC

Estimated Accrual:

Total Accrual at MDACC:	60
Estimated monthly accrual at MDACC:	1-2

Accrual Comments:

Is this an NCI-Cancer Therapy Eval	on Protocol (CTEP)? No
------------------------------------	------------------------

Is this an NCI-Division of Cancer Prevention Protocol (DCP)? No

Statistical Considerations:

The primary objective for this phase II study is to estimate the efficacy and evaluate the toxicity

of the single agent Carfizomib when given to patients with relapse/refractory mantle cell lymphoma (MCL). The maximum number of patients will be enrolled is 60.

The overall response (OR: complete response + partial response) at 4 cycles and toxicity at 1 cycle will be monitored simultaneously using the Bayesian stopping boundaries calculated based on beta-binomial distribution. Independence is assumed between OR and toxicity. Toxicity is defined as the following toxicities observed during cycle 1 (28 days) of the treatment:

Non-hematologic:

- >/= Grade 2 neuropathy with pain
- >/=Grade 3 non-hematologic toxicity (excluding nausea, vomiting, diarrhea, hyperglycemia due to dexamethasone treatment and rash due to lenalidomide treatment)

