	0.35	0.962
	0.45	0.932
	0.55	0.926
	0.65	0.925

The above stopping boundaries and operating characteristics are calculated using MultcLean (v.2.0.0) design software downloaded from http://biostatistics.mdanderson.org/SoftwareDownload. A sample size of 1000 was used for the historical (standard treatment) data for the Model Input to approximate the fix targets for OR and toxicity rates.

Summary statistics will be provided for continuous variables. Frequency tables will be used to summarize categorical variables. Logistic regression will be utilized to assess the effect of patient prognostic factors on the response rate and the toxicity rate. The distribution of time-to-event endpoints including overall survival and progression free survival will be estimated using the method of Kaplan and Meier. Comparison of time-to-event endpoints by important subgroups will be made using the log-rank test. Cox proportional hazard regression will be employed for multivariate analysis on time-to-event outcomes.

Toxicity data will be summarized by frequency tables for all patients. For the efficacy endpoints, intend-to-treat analysis will be applied to the eligible patients. For the toxicity endpoint, per-treated analysis will be performed to include any patient who received the treatment regardless of the eligibility nor the duration or dose of the treatment received.

Data Safety Monitoring Board / DSMB at MDACC:

Select the name of the data safety monitoring board (DSMB) monitoring this protocol: Not Applicable

Please explain: This protocol is not randomized or blinded.

Protocol Monitoring:

Does this protocol have a schedule for interim and final analysis? Yes

Provide a summary or schedule of interim analysis.

Patients will be monitored by a cohort size of 10 according to the following stopping boundaries for OR at 4 months and toxicity at one month. If the number of responses required for moving the trial to next stage has not been achieved, the patient enrollment will be halted until enough responses observed.

Number of patients evaluated	Stop if = OR observed</th Stop if >/= toxicity observed	Stop if >/= toxicity observed
10	1	6
20	5	10
30	8	14
40	12	18
50	16	21
60	Always stop with this many patients	

Protocol Monitoring Plan:

This study will be monitored by the MD Anderson IND Office and a protocol-specific monitoring plan will be followed.

Intellectual Property:

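### Scheduled survival follow-up omits patients who progress on treatment, so the planned Kaplan-Meier overall survival is probably too high

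*Combined protocol and SAP*

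**What the plan says.** - **Objective.** The secondary objective reads "To estimate the response duration, progression free survival, time to failure and overall survival".
- **Analysis.** Statistical Considerations states: "The distribution of time-to-event endpoints including overall survival and progression free survival will be estimated using the method of Kaplan and Meier". Log-rank and Cox analyses are also planned for time-to-event endpoints. Efficacy is analysed by intention to treat among eligible patients, so patients who progress stay in the survival analysis. No censoring rule for overall survival is given.
- **Treatment end.** Under Proposed Treatment/Study Plan: "Therapy will continue in 28-day cycles for a maximum of 36 cycles (3 years), until there is disease progression, unacceptable toxicity".
- **Last visit.** The end-of-treatment visit is timed in footnote 16 of the Table of Assessments: "Approximately 30 days after discontinuation of all study drugs or before start of subsequent treatment (whichever occurs first".
- **Survival contact.** The row "Disease status and survival" is marked only in the long-term follow-up column, with footnote 17: "Every 6 months for 1 year via telephone. For subjects who did not progress during treatment".
- **Prognosis.** The Study Rationale says: "MCL is not yet curable because most patients eventually relapse and succumb to progressive MCL".

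**The concern.** Kaplan-Meier and Cox both assume that a patient censored at a given time has the same future risk of death as those still followed. Footnote 17 withholds follow-up because of progression, which is itself a prognostic event. Limiting disease-status calls to patients without progression is reasonable, because for the others progression is already recorded. Applying the same limit to survival removes the contact that would find most of the later deaths.

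The survival curve would then rest mainly on deaths before or soon after progression and on patients who stopped for other reasons. The planned log-rank and Cox analyses of survival would use the same censored data; the effect on those comparisons was not computed. Progression-free survival is little affected, because progression on treatment is already the event.

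**Working it through.** **Figures in the plan.** The plan gives no figure for overall survival. Its own sample-size figure reproduces: with Beta(0.9 + 27, 1.1 + 33) the 90% credible interval for response at 60 patients has width 0.206, against the stated maximum of 0.21. The stopping boundaries and all 25 early-stopping probabilities also reproduce. None of these depends on survival follow-up.

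**Step 1: follow-up by reason for stopping.**

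| Treatment ended by | Last scheduled survival contact |
|---|---|
| Progression | End-of-treatment visit, about 30 days after stopping or earlier if new treatment starts |
| Toxicity, withdrawal or completing 36 cycles, without progression | Telephone, 6-monthly for 1 year |

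**Step 2: direction.** Let *q* be the share of progression-free survival (PFS) events that are deaths. With exponential times, the death hazard is *q* × ln 2 / (median PFS) before progression and ln 2 / (median post-progression survival) after it. The two are equal, and the bias is zero, when *q* = median PFS / median post-progression survival. Below that value the bias is upward. In the grid used in Step 4 the lowest break-even is 4/18 = 22%.

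Simulation with equal hazards confirms this: 24-month survival is 0.759 true and 0.759 estimated at a 10% share, and 0.575 and 0.575 at 20%.

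**Step 3: one worked case (all rates assumed).** Median time to progression is 6 months, so λ = ln 2/6 = 0.1155 per month. Median survival after progression is 12 months, so μ = ln 2/12 = 0.0578. The death hazard before progression is *h* = 0.005. True survival is

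S(t) = e^(−(λ+h)t) + [λ/(λ+h−μ)] × [e^(−μt) − e^(−(λ+h)t)]

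- 12 months: 0.235 + 1.841 × (0.500 − 0.235) = 0.72
- 24 months: 0.055 + 1.841 × (0.250 − 0.055) = 0.41

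In simulation, stopping without progression is set at 0.04 per month and patients who progress on treatment are censored one month after progression. Kaplan-Meier then gives 0.85 and 0.65, an excess of 13 and 24 points.

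**Step 4: range.** Assumptions: median PFS 4, 6 or 9 months; median post-progression survival 6, 12 or 18 months; 15% stop for toxicity and receive the year of calls; treatment capped at 36 cycles; patients who progress on treatment censored one month after progression. Bias is Kaplan-Meier minus true survival, in percentage points.

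| Share of PFS events that are deaths | 12 months | 24 months |
|---|---|---|
| 5-10% | 5.1 to 18.3 | 11.4 to 34.8 |
| 20% | 0.8 to 12.5 | 1.6 to 24.8 |
| 30% | −2.3 to 9.6 | −4.7 to 19.2 |

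In the 5-10% case only 23-33% of deaths within 24 months are captured. Repeat simulations agree within sampling noise.

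**Step 5: sensitivity.**
- Censoring at progression itself, possible because footnote 16 allows an earlier visit, widens the 5-10% case to 6.5-26.4 and 14.3-45.9 points.
- Treating toxicity stops as a competing risk gives about 6-21 and 10-38.
- A separate model with 18 scenarios (median time to progression 4, 6 or 12 months; post-progression survival 6, 12 or 24 months; death hazard before progression 0.005 or 0.02 per month) gives an upward bias in every one: about 2-21 points at 12 months and 4-29 at 24.

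**Scale.** With 60 fully followed patients and 50% survival, the Kaplan-Meier standard error is √(0.5 × 0.5/60) = 0.0645, or 6.5 points. In many scenarios the bias exceeds it.

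**The case against.** The supplied text is a protocol abstract. Its assessment table is numbered section 15, and footnote 15 sends the reader elsewhere: "See section 6 for pre-treatment therapy and study drug administration and section 7 for dose modification guidelines". Those sections are not supplied, and one of the missing sections could require survival follow-up for everyone. Neighbouring table rows also lost marks in extraction, so the position of a single mark is weak evidence. This stands as a limit: confidence that no other follow-up rule exists is medium. Footnote 17 is intact, however, and any wider rule would have to be reconciled with it.

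No passage fixes the survival censoring date, and a single centre may learn of deaths from its records. If such deaths were counted while living patients were censored at last contact, the bias could shrink or reverse. That is fair, and this case was not quantified, but the text describes no such process.

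Every rate in the calculation is assumed, and the leading range depends on a low share of deaths among PFS events. This also stands: only the mechanism and the probable direction come from the documents.

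Finally, overall survival is one of four secondary endpoints with no target or decision rule. That limits the consequence. It does not make the estimate sound.

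**Conclusion.** The concern holds for the text supplied. Followed as written, the plan makes censoring of overall survival depend on progression, and no visible procedure collects later deaths. The bias is upward provided the death hazard is higher after progression than before, which the Study Rationale supports but does not quantify. Under the assumed rates it ranges from small to several times the sampling error, and it can turn negative if nearly a third of PFS events are deaths. The point should be fixed, but it does not touch the trial's primary conclusions.

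**What to change.** Amend footnote 17 so that the 6-monthly telephone contact collects survival status for all treated patients, whatever ended treatment, and keep the no-progression restriction for disease status only. State the censoring rule for overall survival in Statistical Considerations.

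In the 5-10% case this takes the 12-month bias to 0.0, as it must once everyone is followed for a year. It cuts the 24-month bias to 1.2-4.1 points and raises capture of deaths within 24 months to 72-87%. One vital-status check of all treated patients at a common cut-off removes the rest; with a 36-month cut-off the simulated bias was 0.0 at both times.

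The cost is one amended footnote with its usual review, about two calls per patient who progressed on treatment (at most 60 × 2 = 120), and at most 60 checks at the cut-off. No visits or procedures are added.

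The abstract page gives the version status as terminated, so an amendment may no longer change data collection. In that case, retrieve vital status for all treated patients from records where permitted, which a single centre makes feasible. Failing that, report the censoring rule and do not present Kaplan-Meier overall survival as unbiased.

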- >/=Grade 3 nausea, vomiting, or diarrhea uncontrolled by maximal antiemetic/antidiarrheal therapy
- >/=Grade 4 fatigue persisting for > 7 days
- Treatment delay greater than 21 days for toxicity

Hematologic:

- Grade 4 neutropenia [absolute neutrophil count (ANC) < 500/mm3] lasting for > 7 days
- Febrile neutropenia (ANC < 1,000/mm3 with a fever >/= $38.3 \cdot \text{C}$)

Grade 4 thrombocytopenia (<25,000/mm3) that persists for >/= 7 days, despite holding treatment Treatment delay greater than 21 days for toxicity

Based on the efficacy and toxicity data from a Phase II study of Velcade in relapse/refractory MCL and two Phase II ongoing studies of Carfizomib in multiple myeloma, we will consider that Carfizomib is promising in treating relapse/refractory MCL if the OR rate at 4 months is at least 45% and the toxicity rate at 1 month is below 30%. A sample size of 60 ensures that, if the trial is not terminated early, a posterior 90% credibility interval for OR ate at 4 months will have width of .21 at most, under the assumption of a 45% OR rate. The prior probabilities of OR and toxicity for the regimen are modeled by beta distributions (*Beta*(0.9, 1.1) and *Beta*(0.6, 1.4), respectively). Denoting the probabilities of OR and toxicity by $\{\theta_{OR}, \theta_{TOX}\}$, and they are compared to fixed targets of OR and toxicity rates. The following decision criteria will be applied:

- 1) stop if Prob{ $\theta_{OR}\!<\!0.45\,|\,data\}\!>\!0.95,$ and
- 2) stop if Prob{ $\theta_{TOX} > 0.30 | data$ } > 0.95

Patients will be monitored by a cohort size of 10 according to the following stopping boundaries for OR at 4 months and toxicity at one month. If the number of responses required for moving the trial to next stage has not been achieved, the patient enrollment will be halted until enough responses observed.

Number of patients evaluated	Stop if ≤ OR observed	Stop if \geq toxicity observed		
10	1	б		
20	5	10		
30	8	14		
40	12	18		
50	16	21		
60	Always stop with this many patients			

The operating characteristics are summarized in the following tables (based on simulations from 10,000 trials).

True Toxicity Rate	True OR Rate	Prob(stop the trial early due to toxicity or futility)
0.10	0.25	0.928
	0.35	0.493
	0.45	0.103
	0.55	0.011
	0.65	0.001
0.20	0.25	0.928
	0.35	0.497
	0.45	0.111
	0.55	0.020
	0.65	0.009
0.30	0.25	0.936
	0.35	0.551
	0.45	0.206
	0.55	0.125
	0.65	0.116
0.40	0.25	0.967
	0.35	0.766
	0.45	0.587
	0.55	0.544

	0.65	0.539
0.50	0.25	0.995

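### At the 30-patient look the written futility criterion gives a boundary of 9 responses but both tables print 8, and no sentence says which prevails at 9 of 30 (minor)

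*Combined protocol and SAP*

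**What the plan says.** Everything is in Statistical Considerations, with the boundary table repeated under Protocol Monitoring.

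- **Criterion.** The response (OR) rate has prior Beta(0.9, 1.1) and the toxicity rate Beta(0.6, 1.4). Of these rates the text says "they are compared to fixed targets of OR and toxicity rates", and then "The following decision criteria will be applied": stop if Prob(θ_OR < 0.45 | data) > 0.95, and stop if Prob(θ_TOX > 0.30 | data) > 0.95.
- **Table.** "Patients will be monitored by a cohort size of 10 according to the following stopping boundaries". At 10, 20, 30, 40 and 50 patients the trial stops with at most 1, 5, 8, 12 and 16 responses, or with at least 6, 10, 14, 18 and 21 toxicities. The next sentence also works in counts: "If the number of responses required for moving the trial to next stage has not been achieved", enrolment is halted.
- **Source of the table.** "The above stopping boundaries and operating characteristics are calculated using MultcLean (v.2.0.0) design software". On the number of historical patients entered, the section adds that a figure "of 1000 was used for the historical (standard treatment) data for the Model Input to approximate the fix targets for OR and toxicity rates".

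The interim schedule under Protocol Monitoring repeats the table without the posterior criterion.

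**The concern.** The plan states its futility rule twice, once as a posterior probability and once as counts. The two should be the same rule, and at one outcome they are not. With exactly 9 responses among 30 patients, the criterion says stop and the table says continue.

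Staff who follow the interim schedule have one answer. Someone who later checks the decision against the criterion that the plan says will be applied gets the opposite one, and could record a deviation although the schedule was followed. A pre-specified stopping rule should not leave that open.

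**Working it through.** **Inputs (all from Statistical Considerations).** Priors Beta(0.9, 1.1) for OR and Beta(0.6, 1.4) for toxicity; targets 0.45 and 0.30; cutoff 0.95; looks every 10 patients; maximum 60; historical sample 1000. The plan does not give the exact form of the historical distribution. I take Beta(450, 550) for OR and Beta(300, 700) for toxicity, that is 1000 × 0.45 and 1000 × 0.30. This is an assumption.

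**Step 1: reproduce the printed table.** Compare the posterior Beta(0.9 + x, 1.1 + n − x) with the historical distribution and stop for futility if Prob(θ_OR < θ_hist) > 0.95; treat toxicity in the same way. This gives OR 1, 5, 8, 12, 16 and toxicity 6, 10, 14, 18, 21, which are all ten printed cells. Adding the trial prior or a Beta(1, 1) to the historical distribution gives the same ten cells.

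**Step 2: apply the criterion as written.** Use the fixed target, so the probability is the Beta(0.9 + x, 1.1 + n − x) distribution function at 0.45.

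| Responses of 30 | Posterior | Fixed 0.45 | Against Beta(450, 550) |
|---|---|---|---|
| 8 | Beta(8.9, 23.1) | 0.9794 | 0.9778 |
| 9 | Beta(9.9, 22.1) | **0.9517** | **0.9491** |
| 10 | Beta(10.9, 21.1) | 0.9011 | 0.8976 |

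The fixed-target boundary is 9. Over all looks the written criteria give OR 1, 5, 9, 12, 16 and toxicity 6, 10, 14, 18, 21, so nine of ten cells match and only OR at 30 differs. The spread of the historical distribution is enough to move 9 of 30 from just above 0.95 to just below it. No toxicity cell moves; the closest is 21 of 50, at 0.9589 fixed and 0.9549 against Beta(300, 700).

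**Step 3: which boundary do the printed operating characteristics describe?** Exact recursion over cohorts of 10, with OR and toxicity independent as the plan assumes: early-stop probability = 1 − (probability that futility is never crossed by 50) × (probability that toxicity is never crossed by 50). With 8 in row 30, all 25 printed values are reproduced (largest difference 0.0005). With 9, OR 0.35 and toxicity 0.10 gives 0.520 against the printed 0.493. The Monte Carlo standard error for 10,000 trials is about √(0.493 × 0.507 / 10,000) = 0.005, so the gap is more than 5 standard errors. The printed table belongs to boundary 8.

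**Step 4: size.** Change from 8 to 9 at toxicity 0.10, where the differences are largest:

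| True OR | Boundary 8 | Boundary 9 |
|---|---|---|
| 0.25 | 0.928 | 0.934 |
| 0.35 | 0.493 | 0.520 |
| 0.45 | 0.103 | 0.119 |
| 0.55 | 0.011 | 0.013 |
| 0.65 | 0.001 | 0.001 |

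Over all 25 scenarios the largest rise is 2.7 points (OR 0.35, toxicity 0.10). The largest fall in expected sample size is 1.5 patients, from 44.2 to 42.7 in the same scenario. At OR 0.45 the largest rise is 1.6 points.

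The chance of arriving at the disputed outcome (no boundary crossed earlier, toxicity below its boundary at 30, exactly 9 responses) runs from 8.5% at toxicity 0.10 to 2.0% at toxicity 0.50 when true OR is 0.35, and from 2.4% to 0.6% when it is 0.45. A trial that continues from 9 of 30 still stops for futility at 40 (3 or fewer of the next 10) or at 50 (total 16 or fewer) with probability 0.68 at OR 0.35 and 0.36 at OR 0.45, counting futility looks only. That is why the net effect is small.

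**The case against.** The best defence is that the documents already make the table the operating rule. Statistical Considerations opens by saying that response and toxicity "will be monitored simultaneously using the Bayesian stopping boundaries calculated based on beta-binomial distribution". The monitoring sentence points to the tabulated boundaries and is repeated as the interim schedule, and the operating characteristics were computed with them. The plan also discloses that a sample of 1000 was used to approximate the fixed targets, which warns a reader that a borderline cell may not match the exact calculation. On this view nothing is wrong in the design as operated, and the harm needs someone to set the table aside and recompute.

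Most of this stands. A reader might infer that the 8 is a calculation error, that the operating characteristics are wrong, or that nothing in the plan tells staff to use the table. The documents support none of these. The 8 follows from the disclosed approximation, the 25 probabilities match it, and the monitoring sentences direct staff to the table.

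The defence does not remove the mismatch itself. The same section still states the criterion in fixed-target form and says that it will be applied. The disclosure does not say that the approximation reverses a decision, and no sentence gives precedence when the two forms disagree.

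**Conclusion.** A minor internal inconsistency, confined to one outcome at one look. The written criterion gives a futility boundary of 9 at 30 patients and both tables print 8, so they give opposite decisions at 9 of 30 with no stated precedence. The fixed-target half rests only on printed inputs. The explanation of the 8 rests on the assumed form of the historical distribution, but each form tried gives about 0.949 at 9 of 30 and reproduces all ten cells. The effect on early stopping is at most 2.7 points anywhere in the printed grid and 1.6 points at the 45% target. The size figures assume independent OR and toxicity, as the plan does.

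**What to change.** Make the criterion and the table agree, in one of two ways.

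1. **Hold to the fixed target, which is the plan's stated intent.** Set row 30 to 9 in both tables and restate the early-stop probabilities for OR 0.25, 0.35, 0.45, 0.55 and 0.65:
   - toxicity 0.10: 0.934, 0.520, 0.119, 0.013, 0.001
   - toxicity 0.20: 0.935, 0.524, 0.127, 0.021, 0.009
   - toxicity 0.30: 0.942, 0.575, 0.220, 0.126, 0.116
   - toxicity 0.40: 0.970, 0.778, 0.594, 0.545, 0.539
   - toxicity 0.50: 0.995, 0.964, 0.934, 0.926, 0.925

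   Cost: one cell in each of two tables, a recomputed 25-cell table, and the small rise in early stopping given above.

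2. **Keep 8.** Restate criterion 1 as the comparison of θ_OR with the historical distribution of sample size 1000 centred at 0.45, in the form actually entered in the software, and add one sentence that the tabulated boundaries apply. Cost: a few sentences; no boundary and no operating characteristic changes.

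The toxicity boundaries stay as printed either way. The abstract page marks this version as terminated, so if it will not be amended, the same clarification belongs in the report of the stopping rule and in any reuse of the design.
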